8.3 ENDPOINTS

8.3.1 Primary Endpoint

MSIS-29 psychological scale (9 questions): Change from baseline to month 12.

8.3.2 Secondary Endpoints

- MSIS-29 psychological scale (9 questions): Change from baseline to month 6
- MSIS-29, full scale: Change from baseline to months 6 and 12
- EQ5D-5L: Change from baseline to months 6 and 12
- Adherence: Proportion of patients with <10% missed injections during 6 and 12 months, measured with the software RDS 2.0
- FSS and MFIS: Change from baseline to months 6 and 12
- HADS: Change from baseline to months 6 and 12
- Working ability: Change from baseline to month 12 will be assessed by recording the following information per patient:
 - I am employed/have my own company
 - 1a. My employment is based on hours/week _____
I work my normal working hours (Y/N)
 - 1b. I now work hours/week _____
 - 1c. For the rest of the time I receive (sickness, activity compensation, parental compensation)
 - I study (indicate how much)
 - I have full sickness (full disability pension)
 - I have retirement
 - None of the above applies to me
- AEs: Proportion of patients with reported AEs at month 12

- Patients satisfaction:
The following question will be answered at the 12 months visit and recorded in the eCRF: “How satisfied are you with the overall treatment and support from health care providers during the last 12 months?”
Categorized as follows: Very unsatisfied / Unsatisfied / Satisfied / Very satisfied
Please specify: _____

- HC Personnel satisfaction:
The following question will be answered once per site at the 12 months visit for the last patient at the site and recorded in the eCRF: “How satisfied are you with the overall treatment and support from health care providers during the last 12 months?”
Categorized as follows: Very unsatisfied / Unsatisfied / Satisfied / Very satisfied
Please specify: _____

- Lifestyle questionnaire: Change from baseline to month 6 and 12 (arm 2)

- Lifestyle goals:
The following questions will be included in the questionnaires completed by the patients before the 12 months visit (arm 2):
 - Was the goal achieved? (Y/N)
 - If yes, better than expected or achieved as expected?
 - If better than expected, a lot or a little better than expected?
 - If no, a little or a lot less than expected?

- Health economy based on QoL and working ability at 12 months

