There is a high unmet need for MS patients to increase their HRQoL and in addition to drugs patients with MS need help to managing their MS. In order to increase patient's stability, adherence and motivation a patient support program, MSP has been developed for Merck AB to increase the well being in patients with MS

Treatment Adherence to MS Therapies

According to the World Health Organisation (WHO), treatment adherence is defined as both compliance (taking the medication in the correct dose and according to the schedule prescribed) and persistency (maintenance of the drug regimen over the long-term).

The degree to which patients adhere to medication regimens is difficult to assess and quantify accurately. There is no standardized tool kit for the measurement of adherence and most studies that have adherence as an outcome use indirect measures. It is clear that poor adherence is an important worldwide problem. The WHO quotes an average figure of 50% for adherence to medication for chronic diseases in developed countries, and in

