6.3.1 Required Medications

Treatment with Rebif® 22/44 mcg as administered by the RebiSmart device and in accordance to the SPC (see Appendix I). The decision to prescribe Rebif® must have been made independently of and prior to considering inclusion into this study.

Patients discontinuing treatment with Rebif® due to any reason during the study period should continue assessments, participation in the support program and perform final visit. The reason for discontinuing Rebif® must be recorded in the eCRF. These patients will be included in the Intention-To-Treat (ITT) analysis and be excluded from the per protocol (PP) analysis.

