8.1 PREDETERMINATION OF SAMPLE SIZE

Assuming a group difference of 14 points (Arm 2 superior to Arm 1) and a standard deviation of 25 points on the primary endpoint a total of 104 patients are required for 80 % power and 5 % significance level with a randomization ratio of 1:1. In order to allow for a 20% drop-out rate 130 patients will be included.

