8.6.5 Missing Data

No data will be imputed; only reported values will be used for the purpose of this analysis.

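### A patient without the single month-12 device download has no adherence result at 6 or 12 months, and the per-protocol set excludes everyone who stops Rebif, although the protocol describes adherence as including persistence

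*Protocol*

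**What the plan says.** The adherence endpoint in Protocol Section 8.3.2 is "Adherence: Proportion of patients with <10% missed injections during 6 and 12 months, measured with the software RDS 2.0". Section 8.6.3 analyses it by logistic regression, separately at months 6 and 12.

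Section 7.1 and the schedule table in Section 7.1.1 place the adherence reading at the 12-month visit only, so the 6-month result comes from the same download. On missing data, Section 8.6.5 says: "No data will be imputed; only reported values will be used for the purpose of this analysis".

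The background in Section 3, citing the WHO, states that "treatment adherence is defined as both compliance (taking the medication in the correct dose and according to the schedule prescribed) and persistency" together make up adherence.

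Under Section 6.3.1, patients who stop Rebif go on with assessments and the support program, attend the final visit and belong to the ITT analysis, but are to "be excluded from the per protocol (PP) analysis". Section 5.4 arranges follow-up on the model of visit 2 for patients who withdraw from the study. Section 8.5 limits ITT to randomised patients with at least one post-baseline questionnaire.

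**The concern.** Adherence is named in the trial title, and the support program is meant to help patients keep to their Rebif treatment. On the protocol's own description, stopping Rebif is a failure of adherence. Patients who stop or withdraw are also those for whom a month-12 download seems most likely to be missing. If the program changes how many patients stop, or how many return for the final visit, the patients with a download are no longer comparable between arms.

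The per-protocol set raises a separate problem. For most endpoints, leaving out patients who stopped the drug is ordinary practice. For an endpoint that includes persistence, it removes patients because of the outcome being measured.

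**Working it through.** **1. The plan's own figures.** The protocol gives no numerical assumption for adherence. Its sample size concerns the primary endpoint: difference 14 points, standard deviation 25, 80% power, 5% level (two-sided reproduces it), 1:1. The noncentral t calculation gives 79.97% power at 51 per arm and 80.7% at 52, so 2 × 52 = 104. Then 104 / (1 − 0.20) = 130. Both stated numbers reproduce and are untouched by this point. Only the 20% drop-out allowance is borrowed below.

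**2. What happens to each kind of patient under the written text.**
- Stops Rebif, attends visit 2, device downloaded: has an outcome, is in ITT, is out of PP.
- Stops Rebif or withdraws, no download obtained: has no device-derived outcome at month 6 or month 12 and leaves both regressions.
- Stays on Rebif, no download (for example device failure): the same loss at both time points.
- Has no post-baseline questionnaire: outside ITT, whatever the device shows.

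**3. Effect on the odds ratio.** Let p be the proportion adherent among patients with a download, and m₁, m₂ the shares without a download in Arms 1 and 2. If no download counts as non-adherent, the rate over all randomised patients is aₖ = p(1 − mₖ), and OR (Arm 2 vs Arm 1) = [a₂/(1 − a₂)] / [a₁/(1 − a₁)]. The protocol gives neither p nor m. Assume p = 0.80 in both arms and 20% without a download overall. The observed-only OR is 1.00 in every row.

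| m₁ / m₂ | a₁ vs a₂ | OR, all randomised |
|---|---|---|
| 20% / 20% | 64% vs 64% | 1.00 |
| 15% / 25% | 68% vs 60% | 0.71 |
| 25% / 15% | 60% vs 68% | 1.42 |
| 10% / 30% | 72% vs 56% | 0.49 |
| 30% / 10% | 56% vs 72% | 2.02 |

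For the 10%/30% row: (0.56/0.44) / (0.72/0.28) = 1.273 / 2.571 = 0.49. With p = 0.90, the 10%/30% and 30%/10% splits give 0.40 and 2.50.

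**4. If observed adherence differs by arm.** Assume 70% in Arm 1 and 80% in Arm 2, so the observed-only OR is (0.80/0.20) / (0.70/0.30) = 1.71. Equal loss of 20% gives 56% vs 64%, OR 1.40: smaller, but in the same direction. A 10%/30% split gives 63% vs 56%, OR 0.75, which reverses it. A 30%/10% split gives 49% vs 72%, OR 2.68.

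**5. The injection count.** At three injections a week, 3 × 52 = 156 are due in 12 months and 3 × 26 = 78 in 6 months. The limits are 15.6 and 7.8, so 16 missed (16/156 = 10.3%) or 8 missed (8/78 = 10.3%) fails. Over the full 12-month window, a patient with a clean log who stops at month 6 has missed 50%; counted only up to the stop, the same patient has missed 0%. Over full windows, a stop at or before 0.9 × 12 = 10.8 months fails the 12-month criterion, and a stop at or before 0.9 × 6 = 5.4 months fails the 6-month one, with no need of the device log.

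**The case against.** A reader might infer that the protocol removes everyone who stops Rebif from the adherence analysis. It does not. Section 6.3.1 keeps them in assessments, at the final visit and in ITT, and Section 5.4 provides visit-2-type follow-up after withdrawal. Loss requires that no download is obtained. This stands, and it limits the point to patients without a download, those without a post-baseline questionnaire, and the PP set.

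A reader might also infer that an early stopper with a clean log would be scored as adherent. That needs a rule that counts injections only up to the stop, which the protocol never states. The endpoint's wording reads more naturally as the full 6- and 12-month windows, and such a derivation may properly be left to the SAP. The unstated count is therefore not a finding in itself; it is included in the fix so that the rule is complete.

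It can be said that a recorded stop is itself reported information, so classifying a stopper from it is derivation and not imputation. That is arguable for known stoppers. It does not help a patient with neither a download nor a recorded stop, and a SAP that scored such a patient as non-adherent would conflict with Section 8.6.5.

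Finally, excluding stoppers is an ordinary PP rule, and no section makes PP the main set for adherence. That is correct, so the selection problem affects only adherence results reported in PP.

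**Conclusion.** The point holds in this limited form. The single scheduled download and the reported-values rule together remove any patient without a download from both adherence regressions, and the stated PP exclusion selects on the outcome for this endpoint. These follow from the protocol's own text; they are not gaps that a SAP could fill without departing from it.

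Size and direction are unknown. The range of 0.49 to 2.02 against an observed-only 1.00 rests on assumed rates (80% adherent among downloads, 20% without a download overall, splits up to 10%/30%) and on counting no download as non-adherent. It shows sensitivity and is no forecast. With equal observed adherence and equal loss, nothing changes. The documents do not support a claim that the bias favours either arm. This is one of 13 secondary endpoints in the synopsis, though adherence is in the title; the primary analysis and the sample size are unaffected. The change is a worthwhile, cheap improvement.

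**What to change.** For the adherence endpoint only, amend Sections 8.3.2, 8.6.5 and 6.3.1, and carry the rules into the SAP:

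- Analyse all randomised patients, without the questionnaire condition of the ITT definition.
- Count missed injections over the full 6- and 12-month windows, with injections due after a permanent stop counted as missed.
- Where there is no download but a stop is known, classify the patient from the recorded stop when it decides the result.
- Score any other patient without a download as non-adherent in the main analysis, and give the available-case analysis as sensitivity. Report the number without a download by arm.
- Exempt this endpoint from the reported-values rule and from the PP exclusion of patients who stop Rebif.

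The cost is wording plus one data item. Section 6.3.1 requires only the reason for stopping in the eCRF; Section 9.8 places the date in the patient file, so it must be transferred to the eCRF. Adherence rates will look lower, and some patients whose device merely failed will count as non-adherent; the sensitivity analysis shows how much this matters.

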8.3.3 Safety Endpoints

Any adverse event will be recorded by the nurse at visit 2 (12 months). The proportion of patients with adverse events reported will be compared between the two study arms.

8.4 FURTHER POINTS OF INTEREST

8.5 ANALYSIS SETS

The Intent-to-Treat (ITT) population is defined as all patients randomized into the trial and have completed at least one post-baseline assessment of the questionnaires.

The PP population is defined as all patients randomized into the trial and who are protocol compliant (compliance covers such considerations as exposure to treatment, availability of measurements and absence of major protocol violations).

The Safety Population is defined as all patients randomized

Full descriptions for the criteria for each population (e.g. definitions of major deviations) will be presented in the Statistical Analysis Plan.

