6.4 METHOD OF BLINDING

At visit 1, the patients will complete all questionnaires (except for the Lifestyle questionnaire), i.e. before allocation to study arm which will be performed by Health Solutions during the first week. The questionnaires will be sent for data entry to a unit within Health Solutions which is separate to the unit providing the patient support. At 6 and 12 months the questionnaires will be sent out directly to the patients for completion and the patients will return completed questionnaires to the separate unit at Health Solutions for data entry. The entered data will be transferred to an external vendor for data management and statistics. Thus, the Investigator/Study nurse will be blinded with respect to study arms unless the patient actively reveals it to the Investigator/Study nurse. In the patient information the patients will be asked not to reveal which study arm they are allocated to.

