7 TRIAL PROCEDURES AND ASSESSMENTS

7.1 SCHEDULE OF ASSESSMENTS

Prior to performing any trial assessments that are not part of the patients' routine medical care, the Investigator will ensure that the patient has provided written informed consent. Date of informed consent signature must be recorded in the eCRF.

Visit 1, baseline (Investigator visit)

- Patients who fulfill all eligibility criteria and sign the ICF will be included in the study
- The following patient characteristics are recorded in the eCRF:
 - Age (years)
 - Sex
 - Education
 - Marital status and housing situation
 - Medical history
 - Concomitant medication
 - Working ability
- Questionnaires:
 - All study questionnaires except for the lifestyle questionnaire will be handed out and completed by the patient at the clinic at the time of the baseline visit.
 - After completion the patient will hand in the questionnaire to the nurse at the clinic who will check for completeness and send it to an external vendor for data entry.
 - Lifestyle questionnaire: For patients randomized to the MSP arm, a web based form will be filled out during the first study week (Arm 2).
- Randomization: The Investigator/nurse at the clinic will send patient details of the included patient to Health Solutions who will randomize the patient and provide support to the patient according to randomization.
- Lifestyle goal(s): Personal lifestyle goals will be defined and recorded in the health diary during the first study week (Arm 2).

Six months assessment

- At six months after study entry the patients in both arms will receive questionnaires from the external vendor (Health Solutions) to be filled in and sent back to the vendor.
- For patients randomized to the MSP arm the web based lifestyle questionnaire is completed.

Visit 2, month 12 (Study nurse visit)

- Before the 12 months visit, the patients in both arms will receive questionnaires from the external vendor to be filled in and sent back to the vendor before the visit at the clinic.
- For patients randomized to the MSP arm, the web based lifestyle questionnaire is completed before the visit.
- Working ability will be recorded in the eCRF.
- Adherence data will be downloaded from the RebiSmart device.
- Any adverse event will be recorded in the eCRF.
- Health care personnel satisfaction will be recorded in the eCRF once per site, at the 12 months visit for the last patient at the site.

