7.1.1 Treatment Period

The study period for each patient is 12 months. Study visits and schedule of assessments are summarised in the table below.

VISIT	Baseline Visit 1 (Investigator)	6 month Assessment	12 month Visit 2 (Study nurse)
Clinical assessments			
Informed consent signature	X		
Patient characteristics ¹	X		
Working ability	X		X
Concomitant Medication	X		X
Questionnaires ²	X	X	X
Randomization	X ³		
Lifestyle Questionnaire ⁴	X	X	X
Lifestyle Goals ⁴	X		X
Patient satisfaction			X
HC Personnel satisfaction ⁵			X
Adherence to treatment			X
Adverse Events			X
End of Trial Information			X

1. Age, sex, education, marital status, housing situation and medical history
2. MSIS-29, EQ5D-5L, HADS, FSS, MFIS, and MUSIQoL selected questions
3. Performed by Health Solutions during first study week
4. For patients randomized to the MSP arm
5. Once per site, at the 12 months visit for the last patient at site

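### The ITT set requires a completed post-baseline questionnaire; if used for adherence, working ability and patient satisfaction, it can drop randomised patients who have data

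*Protocol*

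**What the plan says.** Protocol section 8.5 sets out three populations.

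- **ITT:** "all patients randomized into the trial and have completed at least one post-baseline assessment of the questionnaires".
- **PP:** randomised and protocol compliant, where "compliance covers such considerations as exposure to treatment, availability of measurements and absence of major protocol violations".
- **Safety:** no questionnaire condition; "The Safety Population is defined as all patients randomized".

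The section then defers detail: "Full descriptions for the criteria for each population (e.g. definitions of major deviations) will be presented in the Statistical Analysis Plan".

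The footnote to the schedule in section 7.1.1 lists the questionnaires as "MSIS-29, EQ5D-5L, HADS, FSS, MFIS, and MUSIQoL selected questions". Working ability, adherence, adverse events and patient satisfaction are separate rows. Section 6.4 gives the route of the forms: "At 6 and 12 months the questionnaires will be sent out directly to the patients for completion". They go back to the vendor, and section 7.1 wants the 12-month set returned before the clinic visit.

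At visit 2, section 7.1 provides that "Adherence data will be downloaded from the RebiSmart device" and "Working ability will be recorded in the eCRF". Section 8.3.2 has the patient satisfaction question answered at that visit and entered in the eCRF. Section 5.4 arranges follow-up on the visit 2 pattern for patients who withdraw. Section 6.3.1 keeps patients who stop Rebif in assessments and the final visit, and places them in the ITT analysis without mentioning questionnaires.

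**The concern.** An intention-to-treat set should be fixed by randomisation. Here entry depends on what a patient does afterwards, and patients know their arm. Arm 2 has 13 scheduled calls (7 from the nurse, 6 from the counsellor, section 6.1) from the company that also sends the forms; Arm 1 has technical support only. It is therefore plausible, though not documented, that form return differs by arm.

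For the questionnaire scores the condition costs almost nothing, because a patient with no post-baseline score contributes no outcome to the mixed model. For adherence, working ability and patient satisfaction it can discard observed outcomes. Adherence stands in the trial title beside HRQoL. If patients who return no forms also tend to miss injections, and the strength of that link differs by arm, the adherence odds ratio in the ITT set will not be the one that randomisation would give.

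**Working it through.** **1. The plan's own figures.** Section 8.1 gives a difference of 14, SD 25, 80% power, 5% significance, 1:1 allocation and 20% drop-out.
- Normal approximation: n per arm = 2 × (1.960 + 0.842)² × 25² / 14² ≈ 50.1, rounded up to 51 (102 in total).
- The t-test solution is 51.03, rounded up to 52 per arm, 104 in total, as stated.
- 104 / (1 − 0.20) = 130, or 65 per arm, as stated. The drop-out allowance is 130 × 0.20 = 26.

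The sample size is sound and this point does not alter it. The 26 is an attrition allowance for the primary endpoint. It does not count patients who have device data but no forms.

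**2. Which endpoints can lose observed data.**

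| Endpoint | Source | Needs a mailed form? |
|---|---|---|
| MSIS-29, EQ5D-5L, HADS, FSS, MFIS | Forms at 6 and 12 months | Yes |
| Adherence | Device download, visit 2 | No |
| Working ability | eCRF, visit 2 | No |
| Patient satisfaction | eCRF, visit 2 | No |
| Adverse events | eCRF, visit 2 | No, but an all-randomised Safety Population exists |

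The patients affected have visit 2 data, including those followed up under section 5.4, and returned nothing at either 6 or 12 months. One completed assessment is enough to enter ITT.

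**3. When the comparison is biased.** Within an arm, let a and b be the probabilities of return for adherent and non-adherent patients. The odds of adherence among returners equal the true odds × a/b. Hence

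OR(ITT) = OR(all randomised) × (a₂/b₂) / (a₁/b₁).

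Take true adherence of 80% in both arms (true OR 1.00) and a = 0.95 in both arms; all of these are assumptions.
- b = 0.80 in both arms: 0.76/(0.76 + 0.16) = 82.6% in each arm, OR 1.00. The level is biased, the comparison is not.
- b = 0.60 in Arm 1, 0.90 in Arm 2: 0.76/0.88 = 86.4% versus 0.76/0.94 = 80.9%, OR = 0.60/0.90 = 0.67.
- The reverse: OR = 0.90/0.60 = 1.50.
- b = 0.70 versus 0.85: OR = 0.70/0.85 = 0.82.

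**4. The same effect in patient counts.** Assume 80% adherence among returners in both arms, 50% among non-returners, and device data for everyone. The ITT set then shows 80% versus 80%, OR 1.00.
- *Near-worst case, 18 non-returners in Arm 1 and 8 in Arm 2 (all 26):* Arm 1 (47 × 0.8 + 18 × 0.5)/65 = 46.6/65 = 71.7%; Arm 2 (57 × 0.8 + 8 × 0.5)/65 = 49.6/65 = 76.3%. OR = (49.6/15.4)/(46.6/18.4) = 1.27; reversed, 1/1.27 = 0.79.
- *Smaller case, 6 versus 3:* Arm 1 (59 × 0.8 + 6 × 0.5)/65 = 50.2/65 = 77.2%; Arm 2 (62 × 0.8 + 3 × 0.5)/65 = 51.1/65 = 78.6%. OR = (51.1/13.9)/(50.2/14.8) = 1.08.

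This agrees with step 3. In the 18 versus 8 case the return ratios a/b are (37.6/46.6)/(9.4/18.4) = 1.58 in Arm 1 and (45.6/49.6)/(11.4/15.4) = 1.24 in Arm 2. Then 1.24/1.58 = 0.79, and 1.27 × 0.79 = 1.00.

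**5. Sections 6.3.1 and 8.5 side by side.** Section 6.3.1 includes every patient who stops Rebif in ITT. Section 8.5 leaves out any such patient who returned no form. Both cannot hold for that patient.

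**The case against.** The strongest reply is that no section assigns a set to adherence, working ability or satisfaction. Sections 8.6.2 and 8.6.3 name none, section 8.6.1 names ITT and PP only for baseline tables, and full criteria are left to the SAP. This stands so far as to make the point conditional. A reader might infer that the protocol states these patients are excluded from the adherence analysis; it does not. The inference is still strong: ITT and PP are the only efficacy sets, PP is narrower, and section 6.3.1 speaks of an ITT and a PP analysis. Deferral to the SAP is no answer to the condition itself, which section 8.5 already fixes. An SAP that elaborated it would keep the problem, and one that dropped it would depart from the protocol.

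A reader might also extend the point to all visit 2 data. Adverse events are visit 2 data, but the Safety Population is everyone randomised, so that comparison need lose nobody. Section 8.3.2 does also list adverse events as a secondary endpoint without naming a set.

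The size is open to challenge too, and most of that challenge stands. Treating all 26 expected drop-outs as patients with device data and no form is close to a worst case, since one form suffices for entry and the only scheduled download is at visit 2. Even an OR of 1.27 would be imprecise: the standard error of its logarithm is √(1/46.6 + 1/18.4 + 1/49.6 + 1/15.4) = 0.40, giving an approximate 95% interval of 0.58 to 2.79. Differential return is an assumption, and section 6.4 routes the forms to a unit separate from the one giving support. Section 6.3.1, read alone, also keeps in ITT a group likely to have low adherence. It is therefore too strong to infer that the randomised comparison is broken; it could be biased, in a direction the protocol does not reveal.

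**Conclusion.** The point holds in conditional form. Section 8.5 ties ITT membership to a post-randomisation behaviour unrelated to how adherence, working ability and patient satisfaction are measured. If ITT is the set for these endpoints, randomised patients with data can be dropped. Bias in the comparison requires the link between return and outcome to differ by arm. Under the assumed adherence rates, the discrepancy runs from about 1.00 versus 1.08 (6 versus 3 patients) to 1.00 versus 1.27, or 0.79 reversed (18 versus 8, near the worst case). None of these return or adherence rates is documented.

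The primary mixed model, the sample size and the adverse-event analysis in the Safety Population are essentially unaffected, so this is not a threat to the primary result. It should be corrected because the condition gains nothing for the questionnaire analyses, may distort an outcome named in the title, and conflicts with section 6.3.1.

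**What to change.** In section 8.5, define ITT as all randomised patients, analysed in the arm allocated. Add that each endpoint is analysed in every randomised patient with data for it, whether or not a questionnaire was returned, and name the set for each endpoint in sections 8.6.2 and 8.6.3. Report by arm the number of patients with no post-baseline questionnaire. Reconcile section 8.5 with section 6.3.1, so that both say the same about patients who stop Rebif.

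The cost is a few sentences, with no new data and no change to the sample size. The one drawback is that ITT baseline tables will include some patients who contribute nothing to the questionnaire analyses; giving the number analysed for each endpoint deals with that.
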